A wearable sleep device, WatchPAT, designed for home use has been utilized for the last 5 years clinically in adults. In July of 2016, the FDA approved the use of this device down to the age of 12 specifically for the oxygen saturation and apnea hypopnea index, but not the respiratory disturbance index (>17 years only). We have included the device company provided general description of the device, as well as the descriptions of limitation and use with individuals 12-17 years. As many of the limitations of pediatric use pertain to placement and utilization of the device, we will perform the sleep study while the patients are having their already planned and approved overnight stay in the hospital, and will have the device placed by our study personnel, who will be trained in correct placement and interpretation. Our study team also has extensive experience with similar devices from this company, and they are a supportive and easy to work with company.

Known obstructive sleep apnea or treatment with CPAP will not be an exclusion criteria, however, those individuals already utilizing CPAP at home will be requested to bring it for admission and use it during the WatchPAT study, so that we capture their typical home sleep patterns.

III. Research Methods

A. Outcome Measure(s):

Primary Outcome Measure(s): Activity ratios of the hepatic pentose phosphate pathway, TCA cycle and TG synthesis.

Secondary Outcome Measure(s): Peripheral IR as assessed with a 6.5 hour OGTT, measures of SNS activity, Hepatic fat content, hepatic phosphate profile. Targeted glucose and fat metabolism metabolomics, and untargeted exploratory analysis, gut microbiota profile.

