Description: The metabolic cart measures the amount of air that the subject breathes in and out. The machine attaches to the subject's mouth through a tube, or a plastic bubble that is placed over the subject's head. There is the potential for experiencing claustrophobia from having the plastic bubble over the subject's head. A metabolic cart will be utilized multiple times during the OGTT study day to measure rates of oxygen consumption and carbon dioxide release. These rates can be utilized to calculate rates of carbohydrate and fat oxidation and resting energy expenditure.

Risk: Minimal risk of claustrophobia.

Justification/Minimization: These studies are well tolerated by youth, and involve placing a clear plastic hood over the subjects head for approximately 20 minutes. The data collected from the baseline study is also very useful for assisting obese subjects in determining their true caloric needs, and useful in setting dietary goals for weight loss. This piece of information is thus utilized in post-study nutritional counseling.

13. Food Frequency Questionnaire (SEARCH FFQ)

Description: Customary macronutrient pattern will be ascertained by diet interview at the time of admission using a SEARCH FFQ, modified to incorporate common food choices among ethnically and regionally diverse youth aged 10-19 participating in another large childhood diabetes study, SEARCH (48). The instrument is self-administered with staff support to provide instructions, answer questions, and to review the form after completion, and captures the last week of dietary intake.

Risk: None

Justification/Minimization: Several of the measurements being assed are affected by prior nutritional intake. Furthermore, subjects will receive dietary counseling at the end of the study, and by knowing

what their previous dietary pattern is, suggestions for improvement can be tailored to their specific dietary habits.

14. 3DPar Questionnaire

Description: A questionnaire (3DPAR) recalling the physical activity levels of the three previous days will be completed at visit 3. screening.

Risk: None

Justification/Minimization: Physical activity can directly affect insulin sensitivity, our primary outcome measure. The 3DPar is a well validated measure to asses 3 days of physical activity in youth, and includes a variety of youth centric activities.

15. Strengths and Difficulties Questionnaire:

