The protocol as described includes the entire subject set, which allow for comparisons between obese girls with and without PCOS. OGTT with an oral tracer will be conducted in all subjects. The specific points that are to be evaluated are listed below:

- 1) OGTT with glycerol tracers
 - a. Purpose: Develop an oral stimulus model to assess hepatic substrate flux
 - i. Question 1. Is 6.5 hours post oral load long enough to model hepatic and adipose insulin sensitivity?
 1. Rationale: In our current study (14-0542), we have found that 6 hours are required for metabolites to return to normal, we do not anticipate this to change greatly with the addition of the glycerol tracer.
 2. Measurement. Serum glucose and insulin will be measured post-glucose load for 6.5 hours in the first 6 subjects. If 6.5 hours post glucose values are within 20 mg/dL for glucose and 20 IU/mL for insulin relative to baseline values, 6.5 hours will be considered sufficient.
- 2) Measurement of Hepatic Substrate flux in youth.
 - a. Purpose: Optimize a model to asses hepatic substrate flux in youth looking at shifts from pentose phosphate pathway (PEP), TCA cycle and fatty acid synthesis
 - i. Rational: utilizing an oral glycerol model with NMR isotopomer analysis is a newer technique. It has not been validated in youth.
 - ii. Measurement: NMR isotopomer analysis with pathway flux calculations and modeling
 - iii. Revision plan if model not correct: 1) increase the amount of tracer given 2) increase the frequency of blood draws in the later sampling period.

Overall Project Limitations:

- 1) Subject recruitment is always a potential concern, but is minimized by a streamlined recruitment system and experience with this population; the previous, more intensive study is well tolerated in youth and enrolled faster than projected. In addition, we had >100 new PCOS referrals to our pediatric endocrinology department in 2013 alone, and the PI has a clinic specifically for girls with PCOS.
- 2) Subject drop-out: We expect reasonably good completion rates due to the non-invasive nature of the two study visits and our low dropout rate in our previous studies in control and PCOS adolescents using similar procedures.

V. Data Management and Security Plan

Data Entry

Data will be entered from paper forms. Once forms are completed, verified and corrected for inconsistencies, they will be manually entered at our site using a computerized data management system (Redcap).

Edit Checks

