Power calculation: The primary outcome is hepatic substrate flux pathway percentages measured as PEP, TCA and TG synthesis pathways. Power analysis is based on publications utilizing similar methods, with the Primary Aim of understanding differences in hepatic metabolism in obese girls with PCOS who either have or do not have hepatic steatosis. The reference manuscript included 13 men without HS, and 6 men with HS⁵⁰. They found that during hyper-insulinemia, glycerol related gluconeogenesis was increased, as was the PEP cycle in individuals with HS compared to those without. Utilizing the PEP value, from this paper, the difference between the group means is 3 μ mol.min.kg FFM, and the standard deviation is 2 μ mol.min.kg FFM. Differences between the two primary groups (PCOS, controls) will be assessed with a t test or for non-normally distributed data a non-parametric test such as Mann-Whitney U. With 15 untreated PCOS with HS and 15 untreated PCOS without HS, we would have a power of 0.97 to detect an alpha of 0.05. Since the reference population is men who have more uniform hormone profiles, I am choosing to be overpowered should the variability in our population be greater. As the measurement is in kg of fat free mass, we will not have to do adjustments with BMI or weight. However, as African Americans are less likely to have HS, and Hispanics more likely to have HS, if ethnicity percentages are different between groups, we will need to adjust for ethnicity in our calculations.

Secondary Aims: a) For comparison of the PCOS to control groups, individuals will be matched in terms of HS status, so that the comparison is just between the hormonal state. I am assuming that there will be less of a difference between these groups, so with a difference of 2 Umol.min.kg FFM, and the standard deviation is 2, with 20 PCOS and 20 controls, we would have a power of 0.87 to detect a alpha of 0.05. b) For comparison of treatment with either metformin or OCP's, we will compare the untreated group to the treatments individually. We will not compare the two treatments to each other. I am assuming that there will be less of a difference between these groups, so with a difference of 2 Umol.min.kg FFM, and the standard deviation is 2, with 30 PCOS and 15 in a treatment group, we would have a power of 0.87 to detect a alpha of 0.05.

All measures will be adjusted for OSA status (yes/no) and/or severity of AHI.

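### The primary outcome is a ratio or percentage, but the 0.97 power and the reason for not adjusting for BMI both come from an absolute rate per kg fat-free mass

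*Combined protocol and SAP*

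**What the plan says.** Section III.A (Outcome Measure(s)) gives the primary outcome as "Activity ratios of the hepatic pentose phosphate pathway, TCA cycle and TG synthesis". The power paragraph of section VII (Data Analysis Plan) words it differently: "The primary outcome is hepatic substrate flux pathway percentages measured as PEP, TCA and TG synthesis pathways". Neither section states the numerator and denominator of the ratio or percentage.

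The same paragraph then sizes the study on another quantity. It begins "Utilizing the PEP value, from this paper", where PEP is the plan's label for the pentose phosphate pathway (section IV: "looking at shifts from pentose phosphate pathway (PEP), TCA cycle and fatty acid synthesis"). It continues that "the difference between the group means is 3" and gives the unit and spread as "mol.min.kg FFM, and the standard deviation is 2". The source is a study of 13 men without HS and 6 with HS, measured during hyperinsulinaemia. With 15 untreated PCOS girls with HS and 15 without, the plan states power of 0.97 at alpha 0.05.

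The rule on body size follows from that unit: "As the measurement is in kg of fat free mass, we will not have to do adjustments with BMI or weight". Adjustment for obstructive sleep apnoea is planned, and for ethnicity if its distribution differs between groups.

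The two secondary power statements (PCOS against control, and each treatment against untreated) assume a difference of 2 and SD of 2 in the same unit, and state power of 0.87.

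**The concern.** A ratio or percentage is not expressed per kg of anything. An effect size and SD for an absolute rate therefore say nothing directly about it, and a rule justified by division by fat-free mass loses its premise.

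Two things are at stake. First, the plan describes itself as deliberately overpowered, and that reassurance has no documented basis for the outcome it names. Second, HS is not randomised. Girls with and without HS may differ in adiposity, and the plan sets BMI aside for a reason that does not touch that question. Leaving ratio, percentage and rate all in play also allows the scale to be chosen after the data are seen.

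**Working it through.** **1. Inputs.** From section VII: difference 3, SD 2, n = 15 and 15, alpha 0.05. Sidedness is not stated; two-sided is assumed because it reproduces the plan's figures and one-sided does not. From section III.B and the enrolment table in III.C: 20 untreated PCOS girls in total.

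**2. Reproducing the plan's figure.** Standardised effect d = 3/2 = 1.5. Noncentrality = d / √(1/n₁ + 1/n₂) = 1.5 / √(2/15) = 4.108, with 28 df and critical t = 2.048. Power is 0.977 (0.984 by normal approximation; 0.991 one-sided by t). The stated 0.97 is reproduced for the per-kg rate.

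Secondary figures: d = 2/2 = 1.0. For 20 against 20, noncentrality is 1/√(2/20) = 3.162 and power 0.869. For 30 against 15, noncentrality is 1/√(1/30 + 1/15) = 3.162 and power 0.871. Both match 0.87.

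**3. What carries over.** Power depends on the outcome only through d. The 0.97 therefore holds for a ratio or percentage if, and only if, d on that scale is also about 1.5. The documents give no mean, difference or SD on either relative scale and no conversion from the rate, so no single corrected figure can be computed. The values of d below are assumptions that show the range (two-sided t test, unadjusted):

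| d on the named outcome | 15 / 15 | 10 / 10 |
|---|---|---|
| 1.5 | 0.98 | 0.89 |
| 1.2 | 0.89 | 0.72 |
| 1.0 | 0.75 | 0.56 |
| 0.8 | 0.56 | 0.39 |
| d needed for power 0.80 | about 1.06 | about 1.32 |

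The 10/10 column is included because 15 + 15 = 30 untreated PCOS girls exceeds the 20 planned. The even split is an assumption. Section VIII reports NAFLD in more than 45% of obese girls with PCOS; 45% of 20 is 9, and a 9/11 split gives almost the same power (0.88 at d = 1.5, 0.56 at d = 1.0).

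**4. The BMI rule.** Its only stated ground is the fat-free-mass unit. Set against the outcome in III.A or VII, that premise is false, because neither a ratio nor a percentage carries that unit. Dividing by fat-free mass would also address only scaling. It would not remove a difference in fat mass between the HS groups. The plan itself treats body size as relevant: III.A lists BMI, waist/hip ratio, DEXA and visceral fat among likely contributors to the outcomes, and the preliminary data in section II relate liver fat in PCOS girls to visceral adipose tissue.

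**The case against.** The strongest reply is that the rate is the intended outcome and that the loose words are ratios and percentages. There is some support. Aim 1 speaks of describing flux, section IV refers to flux calculations and modelling, and III.D.8 says DEXA muscle mass is needed to standardise OGTT results. This reading is possible, which is why the remedy is to name a scale and not to assume one. But no section names a per-kg rate as primary, and both sections that define the primary outcome use a relative measure.

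A second reply is that the plan built in a margin for greater variability and openly says its reference population is male. On the rate scale that is fair at 15/15: power stays at 0.80 up to an SD of 3/1.06 = 2.83, about 41% above 2. At 10/10 the limit is 3/1.325 = 2.26, about 13% above 2. Neither margin speaks to a change of scale.

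A third reply is that a unit-free outcome may need no scaling for body size anyway. That stands as far as scaling goes, but it is not the reason the plan gives, and it leaves confounding open.

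Some stronger readings do not hold:
- **That the study is underpowered.** The documents contain no ratio-scale effect from which to conclude this.
- **That the HS comparison is confounded by adiposity.** No table shows BMI by HS status. The nearest data, by sleep-apnoea group, show hepatic fat of 10.5 against 5.3 at BMI percentiles of 98 and 97, which is indirect.
- **That BMI must enter the primary model.** The plan's proposed mechanism links liver fat to adipose insulin resistance and visceral fat, so adiposity may be confounder or pathway. That is a judgement for the investigators.
- **That there is a third primary outcome.** III.D.14 says "Physical activity can directly affect insulin sensitivity, our primary outcome measure", but this is a stray phrase in a questionnaire rationale. III.A lists peripheral insulin resistance as secondary, and the phrase affects neither the power nor the BMI rule.
- **That dosing the tracer per kg matters here.** The documents tie it to no effect on a ratio or percentage.

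**Conclusion.** The point holds as a mismatch of scale, not an arithmetic error. The 0.97 is correct for an absolute PEP rate per kg fat-free mass. For the outcome the plan names, it is conditional on a standardised HS effect of about 1.5 that appears nowhere in the documents. Over assumed effects of 0.8 to 1.5, unadjusted power runs from 0.56 to 0.98 at 15/15 and from 0.39 to 0.89 at 10/10. The secondary powers of 0.87 share the condition, at a standardised effect of 1.0. The stated reason for not adjusting for BMI or weight does not apply to a ratio or percentage, and on no scale does it deal with confounding. Confounding by adiposity remains a risk that the plan has not addressed, not a demonstrated bias. These results assume a two-sided t test and no covariates.

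**What to change.** 1. Name one primary variable, with its unit and (if relative) its numerator and denominator, in identical words in III.A and VII.
2. If it is a ratio or percentage, restate power as conditional on the standardised difference and on the HS and no-HS group sizes the enrolment plan will deliver. At 15/15: 0.98 at d = 1.5, 0.75 at d = 1.0, and 0.80 needs d of about 1.06. At an assumed 10/10: 0.89, 0.56, and about 1.32. If the per-kg rate is made primary instead, the difference of 3 and SD of 2 can stay, but the group sizes still need to agree with enrolment.
3. Give the two secondary powers of 0.87 the same conditional wording.
4. Withdraw the fat-free-mass unit as the reason for not adjusting for BMI or weight. Report the HS comparison without and with BMI or DEXA fat mass as a sensitivity analysis, fixing in advance which of the two is used. Justify the choice of primary adjustment on its own grounds.

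Both body-size measures are already collected, so no new data are needed. The cost is rewording, a less favourable power statement and one extra analysis.

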Likely contributors to above measures: Lipid/glucose markers:(fasting C-peptide and lipid panel, HbA1c); hepatic markers:(c-reactive protein, glucagon, GLP-1 and leptin at baseline, 5 min and 30 min post glucose load to asses change with OG, adiponectin, AST, ALT, GGT), sex-steroids:(DHEAS, free and total testosterone, sex hormone binding globulin, progesterone, estradiol); Body size and composition: (BMI, waist/hip ratio, DEXA, hepatic visceral fat via MRI³⁶⁻³⁹), Whole body fat oxidation at rest and following glucose ingestion as measured with a metabolic cart; Physical activity/ diet:(accelerometer, activity survey (3DPAR); Food frequency survey).Questionnaires for presence of obstructive sleep apnea. Questionnaires for perceived mental strengths and difficulty (note there is no assessment of suicidality on this tool). Obstructive Sleep Apnea, to be assessed with an overnight sleep study via WatchPAT.

B. Description of Population to be Enrolled:

Study staff aims to enroll 20 obese girls with regular menstrual cycles, 20 girls with un-treated PCOS, 20 girls with PCOS treated with at least 6 months of Metformin and 20 girls with PCOS treated with at least 6 months of oral contraceptives. The PCOS groups will be compared to 20 obese non-PCOS controls. This is the number of participants needed to be completed statistically, thus more subjects may be enrolled, to allow for screen failures and dropouts. Total enrollment will be up to 100 participants.

Ethnic Categories	Gender		
	Females	Males	Total
Hispanic or Latino	40	0	40
Not Hispanic or Latino	60	0	60
Ethnic Categories: Total of All Subjects	100	0	100
Racial Categories			
American Indian/Alaska Native	5	0	5
Asian	10	0	10

Native Hawaiian or Other Pacific Islander	10	0	10
Black or African American	32	0	32
White	43	0	43
Racial Categories: Total of All Subjects*	100	0	100

Inclusion Criteria:

- 1) Female
- 2) Ages 12-21
- 3) Sedentary- less than 2.5 hours of moderate (jogging, swimming etc) exercise a week.
- 4) BMI equal or greater than the 90th percentile for age and gender
- 5) For PCOS groups: (NIH definition) irregular menstrual cycles at least 1.5 years after menarche and either clinical evidence of hyperandrogenism or elevated Testosterone (above the norms for age/tanner stage) at time of screening or documented prior to initiation of therapy for OCP and metformin groups.

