- 6) For PCOS groups: patients un-treated or currently treated with either Metformin 1500-2000 mg a day or oral contraception (30-35 mcg ethynodiol a day) for at least 6 months, with > 80% adherence confirmed via refill frequency from pharmacy.
- 7) For non-PCOS groups: regular menstrual cycles at least 1.5 years after menarche and no clinical evidence of hyperandrogenism

Exclusion Criteria:

1. Use of medications known to affect insulin sensitivity: oral glucocorticoids within 10 days, atypical antipsychotics, immunosuppressant agents, HIV medications. Nexplanon, Depo-Provera or Mirena progesterone only contraceptives. Dermal patch or vaginal ring contraception methods. For controls only: metformin or oral contraception.
2. Currently pregnant or breastfeeding women. Development of pregnancy during the study period will necessitate withdrawal from the study.
3. Severe illness requiring hospitalization within 60 days
4. Diabetes, defined as Hemoglobin A1C > 6.4%
5. BMI percentile less than the 90th percentile for age and sex. Weight >325 lbs or <84 lbs.
6. Anemia, defined as Hemoglobin < 10 mg/dL
7. Diagnosed major psychiatric or developmental disorder limiting informed consent
8. Implanted metal devices that are not compatible with MRI
9. Use of blood pressure medications
10. Known liver disease other than NAFLD or AST or ALT >150 mg/mL

Rationale for Inclusion of Non-PCOS Subjects

Obese adolescents are at risk of T2D and its complications, reduced exercise capacity, increased liver and visceral fat, muscle dysfunction and cardiovascular dysfunction therefore the tests

performed screening for each of these problems provide useful information to these subjects. Likewise, sedentary subjects of any weight are at increased risk of reduced bone mineral density (BMD), T2D, reduced exercise capacity, increased liver and visceral fat, muscle dysfunction and cardiovascular dysfunction. Therefore, all of the subjects may benefit from the results of DEXA, glucose testing and exercise prescription and dietary counseling.

C. Study Design and Research Methods

Study Calendar	Visit 1 – Screen	Visit 2 –MRI	Visit 3 – Overnight
Consenting and Eligibility Assessment	X		
History & Physical	X		
Intravenous Blood Draw	X		X
Finger Stick Blood Draw		X	
Urine Pregnancy Test			X
Accelerometer Teaching	X		
Gut Bacteria Collection			X
Questionnaires- SEARCH Food frequency, Activity 3DPAR, Strengths and Difficulties and Sleep assessments			X

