DEXA Scan (located in Leprino building)			X
Oral Glycerol Tracer			X
WatchPAT sleep study			X
EndoPat and Dynapulse		X	
MRI of abdomen and liver,		X	
P MRS of Liver (pending scheduling)		X	
Metabolic Cart			X
Total Time of visit (approximately)	2 Hours	2 Hours	24 Hours
Location of Visit	CHCO CTRC Outpatient	UCD Outpatient Brain Imaging Center	CHCO Inpatient Hospital

The study consists of 3 visits - 2 outpatient visits and one overnight inpatient visit. Inpatient visit will last approximately 24 hours, outpatient screening visit approximately 2 hours, outpatient MRI visit approximately 2 hours. The 3 visits would be completed within 4 months' time.

Overall enrollment procedure plan per group

Test Group	Screening	MRI/MRS	Overnight stay	Oral Glycerol tracer	DEXA
Untreated PCOS	25	20	20	20	20
PCOS w/ Metformin	25	20	20	20	20
PCOS w/ OCP's	25	20	20	20	20
Obese Control	25	20	20	20	20
Total	100	80	80	80	80

VISIT 1 (SCREEN VISIT)

Pediatric CTRC Outpatient unit: Participants will begin with a medical screening and physical exam for inclusion/exclusion criteria evaluation. During this visit, patients will review and complete consent documents, have demographics and medical history confirmed, assess allergies and further evaluation of inclusion/exclusion criteria, have blood samples drawn, and have anthropometrics completed. HbA1c, ALT, AST, CBC panel and testosterone panel will be drawn at the beginning of the visit after consent in all subjects. PCOS subjects will have more labs performed for confirmation of PCOS status, if not performed previously.

Screening lab test	Purpose for test
HbA1C	Rule out type 2 diabetes, if > 6.4% subject to be excluded
ALT, AST	Ensure no severe liver disease, if >150 IU subject to be excluded normal subject is excluded
Hemoglobin & Hematocrit (part of CBC)	If subject is Anemic, they will be excluded
Testosterone	Test for hyperandrogenism – required to meet NIH criteria for PCOS
Optional PCOS labs	
PCOS status must be confirmed prior to enrollment in PCOS group. Referring physicians often do not perform the entire recommend work-up for oligomenorrhea (per 2013 Endocrine Society Clinical Guidelines for PCOS). The values are typically expected in PCOS publications	
TSH, total T4	Ensure no hypo or hyperthyroidism causing amenorrhea
LH, FSH	Rule out primary ovarian failure
17-hydroxyprogesterone	Rule out late onset congenital adrenal hyperplasia
DHEAS	Rule out adrenal tumor
Prolactin	Rule out prolactin secreting brain tumor

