1. Serious Adverse Event Definition

Events are divided into those that are not serious (AE) and those that are serious (SAE). The distinction between an SAE and an AE is a regulatory definition established by the FDA, not a clinical definition. The definition of SAE is not always related to clinical severity of the event. For the purposes of this study an AE is considered a Serious (SAE) when it satisfies any one of the following criteria:

- The event results in an inpatient hospitalization (any overnight stay associated with an admission).
- The event results in the prolongation of a hospital stay.
- The event results in permanent or severe disability.
- The event results in death.
- The event is life-threatening.
- Treatment is required to prevent a serious event.

There have been no SAE's in the research groups experience in the Pediatric CTRC. We do not anticipate encountering SAE's; however, we have identified the following as possible SAE's for the purposes of monitoring:

- Infection related to blood draw or IV placement

a) Serious Adverse Event Reporting

Study patients are instructed to contact the clinic with any serious adverse event meeting the above criteria. Each SAE is recorded on the study form and the PI is informed as soon as possible after they occur and preferably within 24 hours of the notification of the clinic staff. This notification should occur even if data are incomplete. Additional data and follow-up information are documented and sent subsequently as an update to the original report. The PI immediately forwards SAE reports to the COMIRB and any other required institutional monitoring committee.

C. Subject Discontinuation Criteria

If a subject experiences any of the following, the subject will be withdrawn from the study.

1. Inability to complete study procedures
2. Abnormal screening labs (LFT's >150 IU, HbA1C>6.4%, Hg <10 mg/dL)
3. Subject becomes pregnant during study

D. Protocol Stopping Criteria

If one or more subjects experience any of the SAE's listed above, the PI will consult with the study staff prior to continuing study visits with subjects. The PI and RSA will consult about the significance of the SAE's and make a recommendation about subject continuation in the study.

VII. Data Analysis Plan:

Overall Project Statistical Plan:

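### Controls are barred for clinical but not biochemical hyperandrogenism, although testosterone is drawn in everyone, so the secondary PCOS–control contrast may be diluted by an unknown amount

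*Combined protocol and SAP*

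**What the plan says.** Section III.B defines the groups. For PCOS, criterion 5 (NIH definition) requires irregular cycles at least 1.5 years after menarche together with "either clinical evidence of hyperandrogenism or elevated Testosterone (above the norms for age/tanner stage) at time of screening", or such a finding documented before therapy in the treated groups. For controls, criterion 7 requires "regular menstrual cycles at least 1.5 years after menarche and no clinical evidence of hyperandrogenism". None of the ten exclusion criteria mentions testosterone.

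Section III.C, Visit 1, states that "HbA1c, ALT, AST, CBC panel and testosterone panel will be drawn at the beginning of the visit after consent in all subjects". In the table of screening tests, the rows for HbA1c, liver enzymes and hemoglobin each say when a subject is excluded. The testosterone row says only "Test for hyperandrogenism – required to meet NIH criteria for PCOS". The withdrawal list in section VI.C names liver tests, HbA1c and hemoglobin among abnormal screening labs, but not testosterone.

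Section VII, Secondary Aims a), describes the PCOS–control comparison: "individuals will be matched in terms of HS status, so that the comparison is just between the hormonal state". It is planned with 20 per group, a difference of 2 and a standard deviation of 2 µmol/min/kg fat-free mass, for a power of 0.87 at alpha 0.05.

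**The concern.** The androgen requirement has two arms for cases, and only one of them is closed to controls. A girl with regular cycles, no clinical signs and testosterone above the age/Tanner norms passes criterion 7, and the screening draw will show the raised value.

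The protocol's own reasoning makes this relevant. Section II.b links the combination of obesity and hyperandrogenism to altered fat metabolism, steatosis and insulin resistance, and the legend of Figure 1 marks mechanisms influenced by hyperandrogenism. If those mechanisms act in such a control, her flux lies nearer to that of the PCOS group and the estimated difference shrinks. At stake are the size and the power of the contrast in secondary aim (a), and what a small or null difference there would mean.

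**Working it through.** **Inputs from section VII, Secondary Aims a):** 20 PCOS and 20 controls, difference 2, SD 2, alpha 0.05, t test. Sidedness is not stated.

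**Inputs not in the documents (assumptions):** the share *f* of controls with elevated testosterone, taken as 10% or 20% (2 or 4 of 20), and the fraction *c* of the PCOS effect on flux that each carries, taken as one half or all.

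**Step 1. Reproduce the stated power.** The noncentrality is difference / (SD × √(1/n₁ + 1/n₂)) = 2 / (2 × √(1/20 + 1/20)) = 3.162, with 38 degrees of freedom and a two-sided critical value of 2.024. Power is 0.869, which matches the stated 0.87. A one-sided test would give 0.928, so the plan's figure is two-sided.

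**Step 2. Dilute the difference.** If a share *f* of controls is shifted by a fraction *c* of the effect, the expected difference is 2 × (1 − *f* × *c*). SD is held at 2.

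| Share *f* | Effect carried *c* | Difference | Noncentrality | Power |
|---|---|---|---|---|
| 0 | – | 2.0 | 3.162 | 0.87 |
| 10% | half | 1.9 | 3.004 | 0.83 |
| 20% | half | 1.8 | 2.846 | 0.79 |
| 10% | all | 1.8 | 2.846 | 0.79 |
| 20% | all | 1.6 | 2.530 | 0.69 |

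A mixed control group also has a slightly wider spread. Its variance becomes 4 + *f*(1 − *f*)(2*c*)². With all of the effect carried, and that variance averaged with the PCOS variance of 4, power is 0.77 at 10% and 0.66 at 20%. The table is therefore slightly favourable to the plan.

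**Step 3. Power after the fix.** If affected controls are excluded and replaced, the difference stays at 2 with 20 per group, and power stays at 0.87. If they are left out without replacement, the difference stays at 2 but the control group shrinks:

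- 18 controls: noncentrality 2 / (2 × √(1/20 + 1/18)) = 3.078, power 0.85.
- 16 controls: noncentrality 2 / (2 × √(1/20 + 1/16)) = 2.981, power 0.83.

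**Step 4. Break-even.** Setting the power with all 20 controls equal to the power in step 3 and solving for *c* gives about 0.28 at a 10% share and 0.30 at 20%. Restricting without replacement therefore gains power only if affected controls carry more than about 30% of the PCOS effect. Below that, restriction costs a little power, though it still removes the dilution.

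**The case against.** The strongest reply is that the groups do not overlap. PCOS here needs irregular cycles as well as hyperandrogenism, and controls must cycle regularly. A reader might infer that a control with high testosterone is a misclassified PCOS case. The documents do not support that: she is a non-PCOS control, as the protocol intends. The reply does not remove the asymmetry, however. Criterion 7 already bars regularly cycling girls with clinical hyperandrogenism, who are equally not PCOS. The protocol thus treats androgen excess as disqualifying in a control, and leaves out one of its two forms.

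A reader might also infer that the plan has decided to enrol such girls knowingly. It has not. It is silent on what happens to a control with a high value, and its general statement in section III.D that screening labs serve eligibility leaves room for an unwritten practice. What can be said is that no written rule excludes her.

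The phrase about hormonal state explains why the groups are matched on steatosis and does not promise androgen-free controls. That is fair. But matching on steatosis alone leaves androgen status mixed within the control group.

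Finally, a girl with PCOS may qualify on clinical signs with normal testosterone, so a testosterone limit would hold controls to a stricter biochemical standard than cases. It would also change the question from PCOS against all regularly cycling obese girls to PCOS against those without androgen excess of either kind. This stands, and is why both contrasts should be reported. Testosterone is also recorded as a likely contributor (section III.A) and regression is planned, so the issue could be explored later, but no such analysis is pre-specified for this contrast.

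**Conclusion.** The point holds as a minor one. Criterion 7 leaves biochemical hyperandrogenism open in controls, the measurement needed to close it is already taken, and no rule or pre-specified analysis uses it for the PCOS–control contrast. The direction of any effect, toward zero, follows if raised testosterone moves flux in the way the protocol proposes.

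Its size is unknown. The power values of 0.83 and 0.79 (half effect) and 0.79 and 0.69 (full effect) illustrate assumed shares of 10% and 20%. They should not be read as an established loss, and the full effect is the extreme case for a girl with regular cycles. The stated 0.87 is correct for its own inputs.

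A reader might take the problem to reach the main result, because section VII also calls PCOS and controls the two primary groups. The comparison powered for the Primary Aim is steatosis against no steatosis within untreated PCOS, which contains no controls. Only secondary aim (a) is affected.

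**What to change.** Preferred: pre-specify in section VII that the PCOS–control contrast is reported twice, once with all controls and once restricted to controls whose screening testosterone lies within the age/Tanner norms of criterion 5. This leaves enrolment unchanged and adds only analysis work. At the full difference of 2, the restricted contrast has power of about 0.85 with 18 controls or 0.83 with 16.

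Alternative: add the same testosterone limit to criterion 7 and replace girls excluded by it, which keeps power at 0.87. The cost is a few extra control screen failures. The plan screens 25 controls to complete 20, so these must fit, with all other losses, into five places under the enrolment cap of 100.

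Either way the restricted control population is somewhat narrower, and the report should say so. The choice should be made before results are seen.
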